### **Adherence**

Adherence will be displayed for the CP by genotype and cirrhosis status and for the SP by treatment regimen and cirrhosis status. Summary statistics (n, mean, median, standard deviation [SD], and range) will be generated for continuous variables. Numbers and percentages of patients will be presented for categorical variables.

- Adherence to ABBVIE regimen (% of target dose [adherence=cumulated number of pills taken /(initial prescribed number of pills x planned duration)])
  - >105%
  - >95%-<=105%
  - >80%-<=95%
  - >50%-<=80%
  - <=50%
- Adherence to ribavirin (% of target dose [adherence=cumulated dose taken /(initial prescribed dose x planned duration)])

- >105%
  - >95%-<=105%
  - >80%-<=95%
  - >50%-<=80%
  - <=50%
- Percentage of actual treatment duration in relation to the target duration of ABBVIE regimen taken
- Deviating duration of ABBVIE regimen
  - Early discontinuation (actual duration is shortened for more than 7 days)
  - Not deviated
  - Exceedance (actual duration is prolonged for more than 7 days)
- Method used to document adherence (Interview, Diary)
- Percentage of actual days with treatment with RBV in relation to the planned duration
- Ribavirin earlier discontinued than ABBVIE regimen
- Initial dose of Ribavirin
  - 1000 mg/day
  - 1200 mg/day
  - XXX
- Cumulative dose of Ribavirin (g)
- Dose modifications/termination of RBV [in patients taking RBV, for a patient more than one dose modification and its main reason could be reported, but for each single reason the patient is counted only once] (Total number of patients with lower dose than highest previous dose [including patients who stopped the treatment earlier], Anemia, Nausea/Vomiting, Rash, Other [including patients who discontinued ABBVIE regimen earlier, but did not stop the RBV treatment before the ABBVIE regimen])

In addition to the summary statistics of the adherence variables, logistic regression analyses will be performed for the following adherence variables: "adherence to ABBVIE regimen" in all patients of the CP, "adherence to ribavirin" in all patients of the CP taking RBV, each categorized as follows: >=95%, >80%-<=95%, <=80% to investigate the additional impact of overall treatment adherence on SVR12. The categories may be changed if they are sparsely filled. Adherence will be included as mandatory covariate in addition to the baseline explanatory variables already mentioned above. Also the same methods will be applied as described above.

An overview of Tables is given in Table 9.

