#### **8.2.2 Secondary Objectives**

1. To provide real world evidence for predictive factors of virological response
2. To document the effect of the ABBVIE REGIMEN ± RBV on PROs and work productivity in the German population

---

Confidential Information

3. To describe the pattern of real world use of the ABBVIE REGIMEN ± RBV with respect to different patient and treatment characteristics
4. To evaluate the influence of adherence on treatment outcome in routine clinical practice
5. To describe the tolerability of the ABBVIE REGIMEN ± RBV
6. To collect information on co-morbidities and concomitant medication in the German population

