#### 4.1.2 Secondary Parameters

The secondary effectiveness endpoints are:

- The percentage of patients with virological response (HCV RNA  $< 50$  IU/mL) at EoT (defined as last intake of ABBVIE REGIMEN or ribavirin)
- The percentage of patients with relapse (defined as HCV RNA  $< 50$  IU/mL at EoT followed by HCV RNA  $\geq 50$  IU/mL)
- The percentage of patients with breakthrough (defined as at least one documented HCV RNA  $< 50$  IU/mL followed by HCV RNA  $\geq 50$  IU/mL during treatment).
- Rapid virological response at week 4 (RVR 4, i.e. patients with HCV RNA  $< 50$  IU/mL at week 4)
- Sustained virological response 24 weeks after EoT (SVR24, i.e. patients with HCV RNA  $< 50$  IU/mL 24 weeks after EoT)
- Sustained virological response 48 weeks after EoT (SVR48, i.e. patients with HCV RNA  $< 50$  IU/mL 48 weeks after EoT)
- The number and percentage of patients meeting each and any of the following SVR12 non-response categories:
  - On-treatment virologic failure (breakthrough [defined as above] or failure to suppress [each measured on-treatment HCV RNA value  $\geq 50$  IU/mL])
  - Relapse (defined as HCV RNA  $< 50$  IU/mL at EoT followed by HCV RNA  $\geq 50$  IU/mL post-treatment for subjects who complete treatment [not more than 7 days shortened])
  - Premature study drug discontinuation with no on-treatment virologic failure

- Missing SVR12 data and/or none of the above criteria

Further secondary variables are:

- Type of treatment regimen ( $\pm$  Dasabuvir,  $\pm$  RBV, intended and actual combination, dose and duration)
- Adherence
  - Percentage of the DAA dose taken in relation to the target dose of DAA (cumulative dose taken divided by target dose in percent)
  - Percentage of the RBV dose taken in relation to the target dose of RBV (cumulative dose taken divided by target dose in percent)
  - Percentage of missed RBV treatment days in relation to the target number of RBV treatment days
- Co-morbidities and concomitant medication
- Serious and non-serious adverse events and pregnancy occurrences
- Questionnaires on PROs: e.g. PAM-13, FACIT-Fatigue, PRISM and work productivity and activity impairment (WPAI) questionnaire prior to treatment initiation, at EoT as well as 12, 24 and 48 weeks after EoT

No data will be imputed for any effectiveness or safety analyses except for the analyses of the HCV RNA endpoints and PRO questionnaires (if applicable). For further details see sections 4.2.3 and 4.2.7.2.3, respectively.

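### The RBV adherence score mixes missed doses with prescribed dose changes and early stops, so its odds ratio for SVR12 cannot be read as an effect of patient adherence

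*SAP*

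**What the plan says.** The protocol (8.2.2) sets the secondary objective "To evaluate the influence of adherence on treatment outcome in routine clinical practice". SAP 4.1.2 turns this, for RBV, into "Percentage of the RBV dose taken in relation to the target dose of RBV (cumulative dose taken divided by target dose in percent" and, as a further parameter, "Percentage of missed RBV treatment days in relation to the target number of RBV treatment days".

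The Adherence subsection of SAP 4.2.7.2.1 gives the working formula for the dose measure: "cumulated dose taken /(initial prescribed dose x planned duration". Neither place says that the target changes when the prescribed dose is changed or RBV is stopped.

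The same subsection expects such changes. It tabulates "Dose modifications/termination of RBV [in patients taking RBV, for a patient more than one dose modification and its main reason could be reported", with anemia, nausea/vomiting, rash and other as reasons. It also tabulates the share of planned days on RBV, RBV stopped before the rest of the regimen, the initial dose and the cumulative dose. All of these are descriptive.

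The dose score is then used in a logistic regression "to investigate the additional impact of overall treatment adherence on SVR12", restricted for RBV to core-population patients taking it. The bands are "each categorized as follows: >=95%, >80%-<=95%, <=80" per cent. On the model, the SAP states: "Adherence will be included as mandatory covariate in addition to the baseline explanatory variables already mentioned above".

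**The concern.** Patient adherence is the share of the prescribed dose that the patient takes. The SAP divides instead by the starting prescription carried forward over the whole planned course. A patient whose dose is lowered for anemia and who takes every remaining tablet can therefore land in the same band as a patient who skipped tablets. An upward change has the opposite effect: it raises the score and can hide missed doses.

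The regression cannot separate these patients. Besides the score it contains only baseline covariates. Dose modification and days on RBV are not named for it. Baseline hemoglobin is collected (protocol 9.4.1.1) but is not among the SAP's regression covariates, so susceptibility to anemia-driven reduction is not directly adjusted for.

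The protocol says the adherence results may help physicians manage patients, and the SAP's list of effectiveness outputs titles this table as the impact of adherence to RBV on SVR12. Readers will take the odds ratio as the effect of patients not taking their tablets. If patients with prescribed reductions still respond well, a real adherence effect is diluted. If they differ in prognosis, an apparent effect can arise without any missed dose.

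A smaller defect is that the regression bands overlap at exactly 95%. The top band also absorbs patients above 105%, whom the descriptive table shows separately.

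**Working it through.** The plan states no figure for this point, so there is none to reproduce. The check applies the SAP formula to patients whose behavior is known.

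**Inputs.** The formula and bands come from the SAP Adherence subsection. Planned durations of 12 and 24 weeks come from SAP 3.1. The Adherence subsection names initial doses of 1000 and 1200 mg/day. The size and timing of dose changes are not in the documents. Those below are assumptions for arithmetic only and say nothing about how RBV should be dosed.

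**Decomposition.** Score = (dose taken / dose prescribed at the time) × (dose prescribed at the time / initial target dose). Only the first factor is patient adherence.

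**Every prescribed tablet taken.** The first factor is 1. If the dose is cut by a fraction r for a share s of the planned duration, score = 1 − r·s. The patient leaves the top band when r·s > 0.05 and reaches the lowest band when r·s ≥ 0.20.

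Results for 12 planned weeks with full compliance:

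| Assumed change | After week | Score | Regression band |
|---|---|---|---|
| 1200 to 1000 (r = 1/6) | 4 | (4×1200 + 8×1000)/14400 = 88.9% | middle |
| 1200 to 1000 | 10 | (10×1200 + 2×1000)/14400 = 97.2% | top |
| 1000 to 600 (r = 0.4) | 4 | (4×1000 + 8×600)/12000 = 73.3% | lowest |
| 1200 to 600 (r = 1/2) | 4 | (4×1200 + 8×600)/14400 = 66.7% | lowest |
| 1200 to 600 | 8 | (8×1200 + 4×600)/14400 = 83.3% | middle |
| 1200 to 600 | 11 | (11×1200 + 1×600)/14400 = 95.8% | top |
| RBV stopped | 8 | (8×1200)/14400 = 66.7% | lowest |
| 1000 to 1200 | 4 | (4×1000 + 8×1200)/12000 = 113.3% | top |

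Over 24 planned weeks, halving after week 4 gives (4×1200 + 20×600)/28800 = 58.3%.

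**How long a reduction must last (12 weeks).**
- To leave the top band: more than 0.05×12/r weeks, which is 1.2 weeks for r = 1/2 and 3.6 weeks for r = 1/6.
- To reach the lowest band: at least 0.20×12/r weeks, which is 4.8 weeks for r = 1/2. For r = 1/6 the result is 14.4 weeks, longer than the course, so a one-sixth cut alone never reaches it.

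**Missed doses against prescribed reduction.** A patient with no dose change who skips 26.7% of tablets scores 100 − 26.7 = 73.3%. That equals the score of the fully compliant patient cut from 1000 to 600 after week 4. The score cannot tell them apart.

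**With the dose prescribed at the time as denominator.** Every fully compliant patient in the table scores 100%, and the patient who skips 26.7% still scores 73.3%.

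**The case against.** The strongest reply is that the SAP is open about what it computes. In both places the variable is a percentage of target dose, in graded bands, and the term non-adherent is not applied. The adherence table also shows RBV modifications with reasons, days on RBV, early RBV stops and cumulative dose, so a reader can see how much reduction occurred. Cirrhosis is already a candidate covariate. The analysis is secondary, exploratory and data driven. At the planning values (620 patients, SVR12 of 95%) about 620 × 0.05 = 31 non-responders are expected in the whole core population, and RBV takers are only part of it, so the regression would be imprecise under any definition.

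Much of this stands, and it limits the consequence. It does not fill the gap in the model. The descriptive items are not named as covariates or alternative exposures, backward selection can drop cirrhosis, and the output is presented as an adherence effect. With so few events, a few patients in the wrong band can also move the odds ratio.

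A reader might infer that the regression measures dose reduction instead of adherence, or that every patient with a prescribed reduction is scored as non-adherent. The documents support neither. The numerator is dose taken, so missed doses lower the score as well, and reductions with r·s of 0.05 or less do not leave the top band.

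Limits on the remedy also stand. No section confirms that dose-change dates are recorded, and the listed reasons do not show who decided on a reduction. The day-based measure still counts a prescribed stop as missed days and does not register partly skipped daily doses.

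**Conclusion.** The point holds as a problem of construct and interpretation. Followed exactly, the SAP yields an RBV odds ratio for a mixture of missed doses, prescribed dose changes and early stops, which does not answer the adherence objective. Under the assumed changes, fully compliant patients can fall anywhere from the lowest to the top band: 66.7% for a halving after week 4 of 12, 83.3% after week 8, 95.8% after week 11, and 58.3% for a halving after week 4 of 24.

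How many patients are affected, and in which direction the odds ratio moves, cannot be determined from the documents. The point is confined to the exploratory regression in core-population patients taking RBV and to the label of the score in the adherence table. The primary SVR12 estimate is unaffected. The band overlap touches only scores of exactly 95% and is a matter of tidiness. The change is worth making because it is cheap and serves a stated objective.

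**What to change.** 1. In the adherence table and the regression, label the present ratio as RBV dose received relative to the initial target dose.
2. Where the eCRF dose history allows, derive dose taken divided by dose prescribed at the time, and use that as the RBV adherence covariate. The SAP already plans a cumulative RBV dose, so some dose history should exist, but check this first.
3. Where the history does not allow it, keep the present ratio and add a model with a yes/no indicator for RBV dose modification or termination, taken from the modifications and reasons already tabulated. Run the percentage of RBV treatment days as a sensitivity exposure, and state that it still counts prescribed stops as missed days.
4. Make the regression bands non-overlapping and consistent with the descriptive table (>95%, >80% to ≤95%, ≤80%), and say how patients above 105% are handled.

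The cost is SAP wording, one derived variable and one extra model, with missing values where the dose history is incomplete. Only the analysis changes; treatment does not.

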**Table 8      Overview of Outputs for Primary and Secondary Effectiveness Analysis**

Output Title	Output Short Name	Analysis Population
Virological Response Rates by Genotype and Cirrhosis Status – CP/CPSFU - <country>	tvr_<c>_gc_cp	Core population/ Core population with sufficient follow-up data
Virological Response Rates by Genotype and Cirrhosis Status in Patients who Completed ABBVIE Regimen – CP/CPSFU - <country>	tvr_<c>_gc_cp_ARC	Core population/ Core population with sufficient follow-up data: patients who completed ABBVIE regimen
Virological Response Rates - NCP - <country>	tvr_<c>_ncp	Non-core population
Relapse Rates by Genotype and Cirrhosis Status – CP - <country>	trr_<c>_gc_cp	Core population
Viral Breakthrough by Genotype and Cirrhosis Status – CP - <country>	tvb_<c>_gc_cp	Core population
Non-Response Rates by Genotype and Cirrhosis Status – CP - <country>	tnrr_<c>_gc_cp	Core population
Non-Response Rates by Genotype and Cirrhosis Status in Patients who Completed ABBVIE Regimen – CP - <country>	tnrr_<c>_gc_cp_ARC	Core population: patients who completed ABBVIE regimen
Impact of Patient and Disease Characteristics on SVR12 – CP - <country>	tis_<c>_cp	Core population
Adherence by Genotype and Cirrhosis Status - CP - <country>	tah_<c>_gc_cp	Core population
Adherence by Treatment Regimen and Cirrhosis Status - SP - <country>	tah_<c>_tc_sp	Safety population
Impact of Adherence to ABBVIE Regimen on SVR12 – CP - <country>	tiaa_<c>_cp	Core population
Impact of Adherence to Ribavirin on SVR12 in patients taking RBV – CP - <country>	tiar_<c>_cp_RBV	Core population: patients taking RBV

The layouts of the tables mentioned above are provided in Part II of the SAP (Table Shells).

#### **4.2.7.2.2 Liver Fibrosis Assessment, Co-morbidities and co-infections**

Liver fibrosis assessment will be summarized by visit in a table for CP by genotype and cirrhosis status and for the SP by treatment regimen and cirrhosis status displaying:

- Most recent stage of liver fibrosis (No cirrhosis, Transition to cirrhosis, Cirrhosis)

- Assessment method for liver fibrosis staging (Biopsy, Non-invasive, Clinical/Best guess)
- Time between biopsy assessment and treatment start [months] (continuous)
- Time between biopsy assessment and treatment end [months] (continuous)
- Metavir fibrosis score (0, 1, 2, 3, 4)
- Ishak fibrosis score (0, 1, 2, 3, 4, 5, 6)
- Batts/Ludwig fibrosis score (0, 1, 2, 3, 4)
- Knodell fibrosis score (0, 1, 3, 4)
- Scheuer fibrosis score (0, 1, 2, 3, 4)
- Time between FibroScan assessment and treatment start [months] (continuous)
- Time between FibroScan assessment and treatment end [months] (continuous)
- FibroScan [kPa] (<8.8, 8.8-<9.6, 9.6-<14.6, ≥14.6)
- Time between ARFI assessment and treatment start [months] (continuous)
- Time between ARFI assessment and treatment end [months] (continuous)
- AFRI [m/s]
- Time between FibroTest assessment and treatment start [months] (continuous)
- Time between FibroTest assessment and treatment end [months] (continuous)
- Results of FibroTest (<=0.21, 0.22-0.27, 0.28-0.31, 0.32-0.48, 0.49-0.58, 0.59-0.72, 0.73-0.74, >=0.75)
- Esophageal varices (Yes, No, Unknown)
- Child Pugh Score (categorized as 5-6, 7-9, 10-15)

#### **4.2.7.2.3 Quality of life**

Quality of life will be analyzed for CP by cirrhosis status (cirrhosis vs transition to cirrhosis/no cirrhosis) and treatment regimen (2DAA w/o RBV, 2DAA + RBV, 3DAA w/o RBV and 3DAA + RBV).

#### **Pictorial Representation of Illness and Self-Measure (PRISM)**

The burden of suffering can be evaluated by using PRISM (Pictorial Representation of Illness and Self-Measure), which is a brief quantitative method to assess the perceived burden of suffering due to illness. The PRISM tool consists of an A4-size metal board, which stands for the patient's life and a yellow disk, representing the patient, is fixed at the bottom right-hand corner. The patient is asked to reflect the importance of the illness in his/her life by placing a red disk, which represents his/her illness, on the metal board. The distance between the center of the "self" and the illness disc is called "self-illness separation" SIS and is measured in cm (range is 0-27).

A summary table will show descriptive statistics (n, mean, median, SD, minimum and maximum) for the SIS for baseline and the post-baseline time points, as well as changes from baseline, by cirrhosis status and treatment regimen. In addition, analysis of covariance (ANCOVA) will be applied to investigate the effect of the different ABBVIE REGIMENS (± RBV) by cirrhosis status on SIS using the corresponding SIS baseline values as covariates.

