#### Target Population [TP]

Patients will be included if the following applies:

- Age at least 18 years
- Confirmed CHC with genotype 1 and/or 4 only, receiving combination therapy with the interferon-free ABBVIE REGIMEN  $\pm$  RBV. The prescribed ABBVIE REGIMEN needs to be known.
- Have voluntarily signed and dated a patient authorization to use and/or disclose his/her anonymized health data prior to inclusion into the study
- Must not be participating or intending to participate in a concurrent interventional therapeutic trial

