**Core Population [CP]**

The core population is defined as all patients of the target population (TP) (definition see above), who are adequately treated according to the standard of care and within local label recommendations for their specific disease characteristics (cirrhotic status, genotype). The following patients will be excluded from the CP:

- Patients with unknown fibrosis status
- Cirrhotic patients with genotype 1a not receiving ribavirin
- Patients with genotype 1 for whom 2DAA instead of 3DAA is prescribed
- Patients with genotype 4 not receiving RBV

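### In the core population the PRO ANCOVAs compare regimens that the exclusion rules tie to genotype, without adjusting for genotype, and one of the four groups is empty by definition

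*SAP*

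**What the plan says.** SAP 4.2.7.2.3 analyses the questionnaires in the core population (CP) by cirrhosis status and "treatment regimen (2DAA w/o RBV, 2DAA + RBV, 3DAA w/o RBV and 3DAA + RBV". Here 2DAA is paritaprevir/r–ombitasvir, 3DAA adds dasabuvir, and RBV is ribavirin. For PRISM, descriptive statistics and changes from baseline come first; then "analysis of covariance (ANCOVA) will be applied to investigate the effect of the different ABBVIE REGIMENS", with or without RBV. The same sentence sets the model up "by cirrhosis status on SIS using the corresponding SIS baseline values as covariates"; no other covariate is named. The FACIT-Fatigue paragraph, and the PAM-13 paragraph in 4.2.7.2.4, specify the same model. WPAI has no ANCOVA.

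SAP 4.2.1 defines who can be in these analyses. The target population admits "Confirmed CHC with genotype 1 and/or 4 only". The CP keeps patients treated "within local label recommendations for their specific disease characteristics (cirrhotic status, genotype" and lists four exclusions. The first is an unknown fibrosis status. The second is "Cirrhotic patients with genotype 1a not receiving ribavirin". The third reads "Patients with genotype 1 for whom 2DAA instead of 3DAA is prescribed", and the last one is "Patients with genotype 4 not receiving RBV".

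For SVR12, SAP 4.2.7.2.1 treats the matter differently. Genotype and prior treatment status are candidate covariates, and regimen is considered only in further models within subgroups, with RBV versus no RBV in cirrhotic genotype 1 (G1) patients as an example.

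**The concern.** The regimen comparison is made in a population selected so that regimen follows genotype. The model handles cirrhosis status, one of the two characteristics that the CP definition names, but not the other. A difference labelled a regimen effect on fatigue, suffering or activation could then be a difference between genotype 4 (G4) and G1 patients, or between subtypes 1a and 1b. This goes beyond the general lack of randomisation, because the SAP's own exclusions remove the overlap that adjustment would need.

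The PRO objective is also at stake. It asks for the effect of treatment on PROs and work productivity, which is first of all a within-patient question. For PRISM, FACIT-Fatigue and PAM-13 the final analysis gives changes from baseline without a confidence interval, and its only inferential method is the between-regimen model.

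**Working it through.** The plan states no sample size, power or effect size for these ANCOVAs, so there is no figure to reproduce. The check applies the listed exclusions to every combination of cirrhosis status, regimen and genotype, and then asks which regimen contrasts remain estimable.

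**Step 1. Who can be in each group.** Inputs: the target population's genotype rule and the CP exclusions in SAP 4.2.1. Subtype 1a is taken as in the SAP's analysis groups, which pool mixed and unknown G1 subtypes with 1a.

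| Regimen | Cirrhotic | Non-cirrhotic |
|---|---|---|
| 2DAA without RBV | none | none |
| 2DAA + RBV | G4 | G4 |
| 3DAA without RBV | G1b | G1a, G1b |
| 3DAA + RBV | G1a, G1b, G4 | G1a, G1b, G4 |

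Patients with both G1 and G4 can appear only under 3DAA + RBV: the G1 rule removes them from 2DAA and the G4 rule removes them from groups without RBV. One of four regimen groups, or 2 of 8 regimen-by-cirrhosis cells, is empty by definition.

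**Step 2. What is estimable once genotype is added.** Within a cirrhosis stratum, take an intercept, two regimen indicators (three regimens remain) and two genotype indicators (G1a, G1b, G4): 1 + 2 + 2 = 5 columns.

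- *Listed exclusions only.* Cirrhotics have 1 + 1 + 3 = 5 occupied cells and non-cirrhotics 1 + 2 + 3 = 6. The rank is 5 in both strata, so all three contrasts are estimable. The 2DAA contrasts are estimable only because G4 can occur under both 2DAA + RBV and 3DAA + RBV.
- *If the label wording also removes G4 on 3DAA + RBV.* The 2DAA + RBV indicator then equals the G4 indicator, and the rank is 4 with 5 columns. Neither 2DAA contrast is estimable. RBV versus no RBV within 3DAA still is.

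The ribavirin contrast within 3DAA is therefore estimable under both readings. In cirrhotics the information comes from G1b alone; in non-cirrhotics it comes from G1a and G1b.

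**Step 3. How much could leak into the ribavirin contrast without adjustment.** Consider G1 patients on 3DAA and suppose that RBV has no effect. Let p1 and p0 be the G1a shares with and without RBV, and d the G1a–G1b difference in follow-up score at equal baseline score. The apparent RBV effect is (p1 − p0) × d. The documents give no shares, so these are assumptions:

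- 0.5 and 0.1: 0.4 d
- 0.7 and 0.1: 0.6 d
- 0.9 and 0.1: 0.8 d
- cirrhotics, where p0 = 0 by rule, with p1 = 0.7: 0.7 d
- RBV use following subtype exactly: 1.0 d

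For 2DAA + RBV versus 3DAA without RBV, the two groups share no genotype. The unadjusted contrast therefore carries the whole G4–G1 difference (G4–G1b in cirrhotics). The documents do not give d or the G4–G1 difference.

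**The case against.** The strongest reply is that this is a secondary analysis in a study that calls its methods descriptive and exploratory, and that protocol section 9.9 concedes confounding from lack of randomisation. The empty group is only the standard four-regimen layout carried over, so it produces an empty column and not a wrong result. Cirrhosis status is handled, changes from baseline are already tabulated, and the ANCOVA is an addition to them. Genotype biases a PRO contrast only if it affects follow-up scores beyond baseline score and cirrhosis, and the documents do not show that it does. The protocol's background section attributes many adverse events to RBV, so a real regimen effect is plausible.

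Much of this stands and limits the point. A reader might infer more than the documents support:

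- *That every regimen effect in this model is really a genotype effect.* This fails for RBV within 3DAA: G1b can be in both groups in both strata, and so can non-cirrhotic G1a. That contrast is confounded, not aliased.
- *That 2DAA versus 3DAA is completely aliased with genotype.* The listed exclusions leave G4 on 3DAA + RBV in the CP. Complete aliasing requires that the label wording removes those patients too, and the label is not in the documents.
- *That the SAP will report p-values for these effects.* It mentions none for this ANCOVA.
- *That within-patient change is not planned.* It is planned for these three instruments; only its confidence interval is unspecified.

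The exploratory label does not settle the matter. It does not make a contrast separable from genotype, and the general limitation does not disclose that the CP rule itself removes the overlap.

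**Conclusion.** The point holds in this form and is worth correcting. In the CP, 2DAA without RBV is empty, 2DAA + RBV is G4 only, and 3DAA without RBV is G1 only (G1b only in cirrhotics). The contrast of 2DAA with 3DAA is wholly or almost wholly G4 versus G1, separable only through any G4 patients on 3DAA + RBV. The RBV contrast within 3DAA is confounded by subtype but recoverable by adjustment.

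The size in score points cannot be derived. Under the assumed shares above, the spurious RBV effect is 0.4 to 0.8 of any G1a–G1b difference, and zero if there is no such difference.

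Two assumptions carry the enumeration. First, regimen groups follow prescription: the G1 rule refers to the prescribed regimen, whereas the safety groups define RBV as taken, so grouping by actual intake could move a few patients. Second, the cirrhotic G1a rule also covers mixed and unknown G1 subtypes, which the exclusion itself does not say. The documents give no cell counts, so whether each estimable contrast has enough patients is unknown. The primary SVR12 result is unaffected.

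**What to change.** In SAP 4.2.7.2.3 and the PAM-13 paragraph of 4.2.7.2.4:

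1. Delete 2DAA without RBV from the CP questionnaire analyses.
2. Limit the ANCOVA contrast to RBV versus no RBV among G1 patients on 3DAA, by cirrhosis status, adjusted for baseline score, G1 subtype and prior treatment status. State that in cirrhotics it rests on G1b patients. Prior treatment belongs in the model because protocol section 9.7.2 names it, with subtype and fibrosis, among the characteristics relevant to the scheduled combination.
3. Report 2DAA + RBV descriptively, and state that its results cannot be separated from genotype 4.
4. Add 95% confidence intervals to the changes from baseline already tabulated, and present these as the result that addresses the PRO objective.

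The cost is SAP wording and simpler models on data already collected. The price is fewer contrasts and a smaller number of patients in the RBV comparison.
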